#### 7.1.3.3. Medical History

Medical history information will be coded to primary system organ class (SOC) and preferred term (PT) using the Medical Dictionary for Regulatory Activities (MedDRA) (version 20.1 or higher). Medical histories will be summarized by system organ class and preferred term. Summaries will be presented as prior disease and concomitant disease, with the prior and concomitant status determined by whether the condition was active (yes/no) at the time of screening. By subject listings will be created for medical history which will include medical history condition, start and end date, and if ongoing. Prior and Concomitant Medications/Treatments

Medications will be coded using the World Health Organization Drug Dictionary (WHO-DD) of March 2017 or higher. Summaries will be performed using the FAS.

Summaries of prior and concomitant medications or treatments will be presented separately. The number (%) of subjects receiving each medication will be summarized using the World Health Organization Anatomical Therapeutic Chemical (WHO ATC) Class code and generic name.

All prior and concomitant medications and treatments (pharmacological and non-pharmacological) will be provided in a data listing. The data listing will include start and end dates (or indication of ongoing), dose, unit, frequency, route, and an indication of whether the medication usage is prior, concomitant or both.

Concomitant procedures will be coded using Medical Dictionary for Regulatory Activities (MedDRA) (version 20.1 or higher). These procedures will be included in subject data listings. The listing will include the date of the procedure, procedure (including system organ class, preferred term, and reported term), indication, major findings, whether the procedure was elective (yes/no), whether the procedure was performed prior to the first dose of study drug (prior/concomitant).

# 7.2. Safety Analyses

No formal hypothesis testing is planned. Baseline is defined as the last available assessment prior to the first infusion of SBC-102.

Listings of all safety data will be produced.

#### 7.2.1. SBC-102 Exposure

Number of weeks exposed to study drug and study drug infusions received will be summarized overall; and any changes in dose will be described in listings, and may also be provided in tabular summaries.

Exposure to study drug (SBC-102) will be summarized by dose and overall. The total number of infusions attempted, the number of infusions completed both without and with a rate change or infusion interruption, the number of infusions where the entire infusion volume was not administered, the number of subjects with an increase, and the number of subjects with a decrease in dosage will be presented. In addition, a summary will be provided showing the number of weeks on specific doses and the number of infusions received on specific doses.

A data listing will be presented, sorted by subject within initial dose of SBC-102, providing the dates, total planned and actual volumes of drug infused, infusion rate and duration of the each infusion along with any modification to the infusion.

#### 7.2.2. Adverse Events and Infusion-Related Reactions

Adverse Events (AE) will be coded by primary system organ class (SOC) and preferred term (PT) using the Medical Dictionary for Regulatory Activities (MedDRA) (version 20.1 or higher). AEs will be determined as occurring from the signing of informed consent and prior to the initiation of SBC-102 (pre-treatment AEs), or as on/after first dose of SBC-102 (treatment-emergent) as described in Section 9.4.8. Pre-Treatment Adverse Events (PTAEs) will be presented in listings only, and Treatment-Emergent Adverse Events (TEAEs) will be presented in summary tables and listings.

Study displays for TEAEs are described below.

#### 7.2.2.1. Overall Summary of Adverse Events

All TEAEs will be presented using summary statistics (E, and n, %), showing the number of events as well as the number and percentage of subjects with the event.

The overall summary will include but not limited to displaying TEAE, AE by severity, AE by relationship, AE requiring dose modification, AE leading to discontinuation from study, infusion associated reactions (IAR), serious AEs (SAE), and the number of subjects who died due to an AE. The overall summary will include both the number and percent of subject with an event and the number of events. These statistics will be prepared for all TEAEs and, separately, for SAEs and IARs.

The relationship f AEs requires some additional consideration:

- The relationship between an AE and the study drug will be assessed as: not related; unlikely related; possibly related; or related. The number of subjects with at least one related AE and subjects with only AEs not related to study drug will be summarized. Related AEs will include those AEs considered 'possibly related' or 'related' by the investigator; and not related AEs will include those AEs considered 'not related' or 'unlikely related'.
- The number of events (E) will be summarized as reported, with no accounting for the most extreme severity or relationship.

#### 7.2.2.2. AEs, SAEs and IARs by System Organ Class (SOC) and Preferred Term (PT)

The frequencies of TEAEs, SAEs, IARs and percentage of patients with events will be tabulated by PT within SOC. Patients are counted once in each SOC and PT. Percentages will be based on the total number of patients in the specific analysis population. SOCs will be listed in order of frequency of occurrence.

Frequencies will also be presented by the classifications of severity and causality. In addition, frequency of AEs, SAEs, and IARs will be presented for time periods spanning the entire course of treatment with SBC-102: from the start of dosing with SBC-102 in this study to 3 months after the first dose; >3 to 6 months; >6 to 12 months; >12 to

Alexion Pharmaceuticals LAL-CL08

18 months; >18 to 24 months; and >24 months. The incidence of AEs leading to study discontinuation will also be summarized.

Summaries of adverse events will be summarized by anti-drug antibody (ADA) status. Subjects who developed ADA vs subjects who did not develop ADA. For subjects who developed ADA, only those AEs reported on or after the first time ADA were identified will be summarized. The number of subjects experiencing any TEAE will be presented overall and by relationship to study drug, with AE specific details presented by SOC and PT, also by relationship to study drug. This table will also be generated for all TESAEs and for all IARs.

Detailed listings of patients who experience AEs, SAEs and IARs will be presented. Detailed listings will include severity and relationship to treatment, seriousness, as well as action taken regarding study treatment, other action taken, and patient outcome. A separate listing of patients who discontinued from the study due to a treatment-emergent AE will also be provided.

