8.8.1 Adverse Events

All reported AEs will be listed from the date of written informed consent until the end of participation in this study. Separate listings of deaths, SAEs and IARs will also be provided. The numbers and percentages of subjects experiencing any AE, any SAE, any IAR, any related AE, any related SAE, and discontinuations due to an AE will be tabulated.

The frequency of subjects with treatment-emergent AEs, SAEs, and IARs by system organ class (SOC) and preferred term (PT) (coded using Medical Dictionary for Regulatory Activities [MedDRA®] version 14 or higher) will be tabulated. Frequencies will also be presented by the classifications of severity and causality. In addition, frequency of subjects with AEs, SAEs, and IARs will be presented for time periods spanning the entire course of treatment with sebelipase alfa: from the start of dosing with sebelipase alfa in this study to 3 months after the first dose, >3 to 6 months, >6 to 12 months, >12 to 18 months, >18 to 24 months and >24 months. As appropriate, additional listings, summary tables and graphics will be generated to evaluate IAR frequency and severity over time. A listing of subjects who withdraw from the study due to AEs will be presented, and the incidence of AEs leading to study discontinuation will be summarized.

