Concomitant Medications/ Therapies		CONTINUOUS														

^{*} All visits will be calculated from Week 0; consecutive infusions must be administered at least 5 days apart.

P Pre-dose

- 1 All physical examinations will include liver, spleen, and lymph node assessments. In addition, digital photographs (full length and abdominal close up) will be obtained at Weeks 20 and 24 and annually thereafter.
- 2 During infusion visits, vital signs will initially be measured pre-dose, every 15 (±5) minutes during the infusion, and every 30 (±10) minutes from 0 to 4 hours post-infusion (see Section 5.1.9). After a year of treatment with no IARs, the post-infusion monitoring period may be shortened from 4 hours to 2 hours.
- 3 If blood volume is limited, refer to Section 5.1.11 for tiered assessments.
- 4 CBC/hematology, chemistry, liver function tests, lipid panel, ferritin, urinalysis and coagulation studies, (see Section 5.1.11). Prior to any dose change, serum lipid, serum liver, hematology, chemistry, ferritin and hs-CRP shall be obtained. Serum lipid and serum liver assessments should be taken 4, 8, and 12 weeks following any study drug or lipid lowering medication dose change.
- 5 Refer to Section 5.1.14 for PK sampling timepoints.
- 6 Weight will be measured at all visits; Recumbent length or height, and abdominal circumference will be measured at every 3 month visits; head and mid-upper arm circumference will also be measured at all every 3 month visits through Week 96
- 7 Abdominal MRI should be considered in subjects receiving general anesthesia and/or sedation for other procedures. The MRI may be conducted at any time from Week 24 through Week 32, and then annually, and should be scheduled at least 3 months after the preceding MRI assessment.
- 8 Repeating assessments will be performed every 2 months through Week 48 and every 3 months thereafter until study completion.
- 9 PK samples will be collected only at the first annual assessment (Week 48).
- 10 Subjects who are on treatment for at least 96 weeks and have been on a stable dose for at least 24 weeks, may transition to an every other week dosing schedule at the same dose they received on the weekly dosing schedule at the discretion of the PI with Sponsor consultation.

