#### 9.4.9.1 Treatment-emergent Adverse Events (TEAEs)

Treatment-emergent AEs (TEAEs) are events with start dates and start times on or after the date and time of the first study drug infusion (SBC-102). All other AEs with complete start dates and start times are considered Pre-Treatment Adverse Events (PTAEs).

Percentages are based on the total number of treated patients.

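### The adverse event and infusion reaction tables over time use unequal periods and a fixed denominator, with no exposure per period, so their trend cannot be read as a change in risk

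*SAP*

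**What the plan says.** SAP 7.2.2.2 plans tables in which the "frequency of AEs, SAEs, and IARs will be presented for time periods spanning the entire course of treatment with SBC-102". The periods run from the start of dosing "to 3 months after the first dose; >3 to 6 months; >6 to 12 months", then from 12 months on to "18 months; >18 to 24 months; and >24 months". Protocol 8.8.1 sets the same periods, but counts subjects with events.

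For the denominator, SAP 7.2.2.2 states: "Percentages will be based on the total number of patients in the specific analysis population". SAP 9.4.9.1 repeats the rule for treatment-emergent events: "Percentages are based on the total number of treated patients". Protocol 8.1 makes treated subjects the default denominator. Nothing sets a different one for the period tables.

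Exposure is handled in SAP 7.2.1. It starts from "The total number of infusions attempted" and summarises infusions and weeks overall and by dose, but not by period. A listing gives the date of each infusion.

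Two design features change exposure over time:

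- Treatment is expected to last at least 18 months and may last up to 3 years (Protocol 3.2.3, SAP 4).
- Under Appendix A, footnote 10, children with at least 96 weeks of treatment and 24 weeks on a stable dose "may transition to an every other week dosing schedule at the same dose they received on the weekly dosing schedule".

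Protocol 8.8.1 also says that, where suitable, "additional listings, summary tables and graphics will be generated to evaluate IAR frequency and severity over time". It names no denominator for these displays, and the SAP does not specify them.

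**The concern.** Safety and tolerability is the primary objective, and infusion-associated reactions (IARs) are the adverse events of special interest. Readers will look at the period tables to see whether reactions fade, persist or grow as treatment continues.

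The figures in those tables depend on four things besides risk: how long the period is, how many infusions fall in it, how many children are still treated, and the fact that a child who has died or stopped still counts in the denominator as having no event. None of the four is shown beside the figures. A change in risk cannot be told apart from a change in exposure, and a real change can be cancelled by one.

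**Working it through.** The documents give no event rate, so there is no planned figure to reproduce. The check asks what the planned tables would show if the risk per infusion were known.

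**Inputs from the documents**

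- Period lengths in months: 3, 3, 6, 6, 6, then open. The 3-year limit leaves 36 − 24 = 12 months of treatment for the last.
- Weekly infusions per child, at 13 per 3 months: 13, 13, 26, 26, 26, 52 (total 156).
- Earliest switch to every other week: Week 96, which is 96 × 7 × 12 / 365.25 = 22.1 months.
- Up to 10 children; percentages on all treated.

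**Assumptions**

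- An IAR risk p per infusion that is constant, independent between infusions and the same for every child. The main case is p = 2%, with a range of 0.5% to 5%.
- The numbers still treated in each period, as shown below.

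**Formula.** Percentage shown = (children treated in the period / 10) × [1 − (1 − p)^k], with k infusions in the period. At p = 2%:

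- k = 13: 1 − 0.98^13 = 23.1%
- k = 26: 1 − 0.98^26 = 40.9%
- k = 52: 1 − 0.98^52 = 65.0%

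**Percentage of children with an IAR, at an unchanged 2% risk**

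| Children treated per period (assumed) | Dosing after month 24 | 0–3 | >3–6 | >6–12 | >12–18 | >18–24 | >24 |
|---|---|---|---|---|---|---|---|
| 10 throughout | weekly | 23 | 23 | 41 | 41 | 41 | 65 |
| 10 throughout | every other week | 23 | 23 | 41 | 41 | 41 | 41 |
| 9, 8, 7, 6.5, 5.5, 5 (averages) | weekly | 21 | 18 | 29 | 27 | 22 | 33 |
| 9, 8, 7, 6.5, 5.5, 5 (averages) | every other week | 21 | 18 | 29 | 27 | 22 | 20 |
| 9, 8, 8, 8, 6, 2 | weekly | 21 | 18 | 33 | 33 | 25 | 13 |
| 9, 8, 8, 8, 6, 2 | every other week | 21 | 18 | 33 | 33 | 25 | 8 |

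The step at month 6 is upward in every row. After that the pattern may rise, stay level or fall.

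**Switch at Week 96.** Weeks 96 to 104 would hold about 4 infusions instead of 8, so the >18–24 month period has 26 − 4 = 22. The figure becomes 1 − 0.98^22 = 36% instead of 41%, so the switch can affect the last two periods.

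**Range of p** (full retention, weekly; 3-, 6- and 12-month periods):

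- 0.5%: 6, 12 and 23%
- 1%: 12, 23 and 41%
- 5%: 49, 74 and 93%

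**Event counts.** Expected IARs in 10 children at 2% are 10 × k × 0.02 = 2.6, 2.6, 5.2, 5.2, 5.2 and 10.4. That is a fourfold rise at unchanged risk, so counting events as well as children does not remove the problem.

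**Adverse events in general.** At an assumed constant 0.1 per month, 1 − exp(−0.1 × months) gives 26, 26, 45, 45, 45 and 70%.

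**A real fall hidden.** If the risk per infusion falls from 4, 4 to 2, 2, 2 and then 1%, the table reads 41% in all six periods, with 5.2 expected events in each.

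**Clustering.** If the same 2% average falls on 3 of 10 children (6.7% each), 0.3 × [1 − (1 − 0.067)^k] gives 18, 25 and 29% for k = 13, 26 and 52. The steps are smaller but remain.

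**With the right denominator.** A constant 2% risk reads 2.0 IARs per 100 infusions in all six periods, whatever the retention or schedule.

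**The case against.** The strongest reply is that the study is descriptive, has at most 10 children and rests no decision on these tables. Every infusion date and every event is listed, so anyone who wants a rate can count it. SAP 7.2.2.1 asks for event counts as well as children. Protocol 8.8.1 leaves room for further displays of IARs over time.

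Much of this stands, and it rules out three stronger readings that a reader might infer:

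- *A constant risk must look like a rising one.* The documents do not support this. The first two periods are equal and so are the next three. On a fixed denominator, deaths, withdrawals, treatment ending between 18 and 24 months and every-other-week dosing all push later figures down.
- *The tables show only numbers and percentages of children.* SAP 7.2.2.1 provides for numbers of events too.
- *Rates cannot be recovered.* They can be, by hand, from the infusion listing in SAP 7.2.1 and the event listings in SAP 7.2.2.2.

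What the reply does not meet is that no summary table supplies the denominator, and the optional protocol displays name none. With up to 156 weekly infusions per child, the count should not be left to the reader. Small numbers also make each child lost weigh more on a fixed denominator. SAP 7.2.3 already requires the number of contributing subjects on its laboratory mean plots, so showing who contributes would be nothing new in this plan.

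**Conclusion.** The point holds as a matter of readability. As planned, the period tables cannot show whether risk per infusion or per month changes during treatment, and they can mislead in either direction. At an unchanged 2% risk per infusion, the last-period figure ranges from 8% to 65% in the scenarios above, depending only on retention and schedule.

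These sizes rest on an assumed risk, on independence between infusions and on assumed retention. Clustering of reactions in a few children would make the steps smaller. The structural facts rest on the documents alone: unequal periods, a fixed denominator and no exposure per period.

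This is a cheap improvement of modest severity. It bears on the primary safety objective, but the analysis is descriptive and the listings hold the missing information.

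**What to change.** In the time-period tables of SAP 7.2.2.2, add for each period:

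- the number of children at risk, used as the denominator for that period's percentages;
- the number of infusions given;
- child-months of observation, with a stated rule on whether the post-treatment follow-up of at least 30 days (Protocol 7.2.2) counts towards the last period.

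Report IARs per 100 infusions, and adverse events and serious adverse events per child-year, beside the planned numbers and percentages. State that the rule of using all treated children does not apply to these tables. The period boundaries can stay.

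The cost is SAP wording, one derivation of exposure by period from infusion dates already collected, and a few table rows. No new data and no change to trial conduct are needed.

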#### 7.2.2.3. Deaths

A listing of patient deaths and cause of death will be produced, if applicable.

#### 7.2.3. Analyses for Laboratory Tests

Observed measurements and changes from Baseline to each study time point in clinical laboratory data will be summarized.

Frequencies of abnormal values relative to the laboratory normal range and clinically significant abnormal values as well as shift tables showing the change from baseline to post-baseline relative to the normal range will be summarized, if sufficient data are available for analysis.

Spaghetti plots for actual, change from baseline, and percent change from baseline will be created for the following parameters: ALT; AST; GGT; total bilirubin; albumin; alkaline phosphatase; total cholesterol; LDL-C; non-HDL-C; HDL-C; triglycerides; hemoglobin; platelets; prothrombin time (PT[INR]); partial thromboplastin time (PTT [INR]); and serum ferritin.

Plots of mean absolute change and mean percent change over time with standard deviations as error bars may be prepared for the following:

- Liver biochemical parameters: ALT/AST, GGT, bilirubin, albumin, alkaline phosphatase
- Lipids: total cholesterol, LDL-C, non-HDL-C, HDL-C, triglycerides
- Other: Hemoglobin, platelets, PT/PTT, serum ferritin
- The number of subjects contributing to each mean value will be presented in each figure

#### 7.2.4. Physical Examination

A summary of findings including liver size, spleen size, and lymphadenopathy at Screening and follow-up will be presented for baseline and each post-baseline visit.

Summaries of liver and spleen will include the percentage of subjects with palpable and non-palpable organ, the regularity (smooth or nodular), and the sensitivity (tender or non-tender). In addition, the abdominal circumference will be summarized as observed, change from baseline, and percent change from baseline.

Summaries of lymphadenopathy will include whether any lymphadenopathy is present (yes/no) and the presence/absence and tender/non-tender status of each of five specific regions: cephalic, cervical, clavicular, axillary and inguinal.

#### 7.2.5. Vital Signs

Within each visit (infusion), descriptive summaries of both maximum and minimum result and both maximum minimum increase from the pre-infusion assessment will be summarized.

Observed values and change from pre-infusion will be presented for the following vital sign parameters:

- Body temperature
- Pulse rate
- Blood pressure
- Respiratory rate

A listing of the vital signs measurements will be also provided.

#### 7.2.6. Electrocardiograms (ECG)

Baseline ECG results will be summarized as the number and percentage of subjects with baseline ECGs whose ECG was normal, abnormal but not clinically significant, and abnormal and clinically significant.

A listing of ECG results, baseline and unscheduled, will be presented by subject, visit, date, and study day.

#### 7.2.7. Denver II Developmental Screening Test (DDST)

The instrument screens children's performance in four developmental domains: personal-social, fine motor-adaptive, language, and gross motor with respect to the age-matched population. The overall results from DDST are expressed as Normal, Abnormal, Questionable, and Untestable.

DDST results will be listed. The results will also be summarized with the number of patients who had the test done and tested 'normal', 'suspect', or 'untestable' by visit for each of the categories. A shift of the change from baseline to post-baseline result will also be summarized; percentages in the shift table will be based on the number of subjects in the FAS with baseline and post-baseline results.

#### 7.2.8. Antidrug Antibody (ADA) Titer

A subject is considered as having been ADA positive if both the initial titer and a confirmatory titer were positive at that visit.

ADA data will be summarized and include both the number and percentage of subjects who become ADA-positive and positive to neutralizing antibodies.

# 7.3. Efficacy Analyses

Efficacy will be examined on the FAS. For the continuous endpoints, the observed values, change from baseline and percent change from baseline at each time of assessment will be summarized, and may include 95% confidence intervals (e.g. for time points with  $\geq 2$  observed data points).

#### 7.3.1. Handling of Dropouts or Missing Data

All data will be analyzed as they were collected in the database. Missing data in general will not be imputed, any imputation techniques, if applied, are described in Section 9.

Proprietary and Confidential 30

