3.2.2.2 Efficacy

The study is designed to confirm the efficacy of treatment with sebelipase alfa in subjects with rapidly progressive disease presenting in infancy. Survival endpoints will include proportion of subjects surviving to 12, 18, and 24 months of age, and other timepoints, as data permit, and estimated median age at death. Survival rates and median age at death derived from this study will be compared to rates/times reported in the literature and previous studies.

Subjects with LAL Deficiency presenting in infancy typically stop growing and this growth failure, in addition to being the predominant clinical feature, is also one of the main contributors to mortality. Improvement in growth is anticipated to be a prerequisite for any beneficial effects of sebelipase alfa on survival. Therefore, efficacy endpoints will include changes from baseline in the following growth parameters:

- Percentiles and/or z-scores, based on WHO child growth standards (WHO Multicentre Growth Reference Study Group, 2006 and 2007), for the following parameters:
 - Weight-for-age (WFA)
 - o WFL or WFH
 - LFA or HFA
 - Head circumference-for-age (HCFA)
 - Mid-upper arm circumference-for-age (MUACFA)
- Dichotomous growth status indicators for underweight, wasting, and stunting based on WFA, WFL/WFH, and LFA/HFA, respectively (UNICEF, 2009)

Note: Given the switch at age 2 years from measurement of length to measurement of height, growth parameters include weight related to both length and height and age related to both length and height.

A successful therapy for LAL Deficiency presenting in infancy should also mitigate the liver and hematological changes associated with the disease. Therefore, the following laboratory parameters will also be included as efficacy endpoints:

- Changes from baseline in aspartate aminotransferase [AST] and ALT levels
- Normalization of hemoglobin levels without requirement for blood transfusion
- Changes from baseline in serum ferritin levels

Additional exploratory efficacy parameters will be investigated to provide supportive evidence of an improvement of LAL Deficiency with sebelipase alfa treatment, and will include changes or percent changes from baseline (or first available assessment if baseline data are unavailable) in:

- Alkaline phosphatase, gamma glutamyltransferase (GGT), albumin, and bilirubin (direct, indirect, and total)
- Liver and spleen size/volume, as measured by ultrasound or magnetic resonance imaging (MRI)

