8.13 Missing or Invalid Data

All data will be analyzed as they were collected in the database.

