# 7. STATISTICAL ANALYSIS

The Alexion Biostatistics Department or designee will perform the statistical analysis of the data derived from this trial. The analysis will be performed using the SAS® Life Science Analytics Framework version 4.7.2 or higher.

No formal inferential statistical testing will be performed. As appropriate, 95% two-sided confidence intervals (CIs) will be calculated around the estimates based on the exact binomial distribution (Clopper-Pearson method) for binomial endpoints and the t-distribution for continuous endpoints. Confidence intervals, where presented, will be considered descriptive and will be provided to facilitate clinical review and interpretation.

All data collected in this study will be provided in subject data listings sorted by subject number; the dose of SBC-102 temporally associated with the data will be included on the listing. Summary tables and/or graphs will be presented for each endpoint, as appropriate to the data, by evaluation time point.

Unless otherwise noted, the following standard conventions will be used for creating descriptive summaries:

- Continuous numeric endpoints will be summarized by providing the number of subjects with non-missing data, the mean and standard deviation (SD) of the data, and the minimum, first quartile (Q1), median, third quartile (Q3), and maximum value. Mean, median values, Q1 and Q3 will be presented with one decimal point more than the original value, SD will be displayed with two decimal points more than the original value will have the same number of decimal points as the original value;
- For categorical endpoints, the number and percentage of subjects with each possible outcome will be displayed. The denominator for percentages will include subjects with missing data.

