#### Table 3: Age and reference date

AGE	REFERENCE DATE	
Age at Enrollment	Date of Signing ICF	
Age at First Dose of SBC-102	Date of First Dose of SBC-102	

In cases where only the month and year are provided for a date, the day for the date will be imputed as 15. Missing month will be imputed as June. In cases where the day is observed but the month is missing, the date will be imputed as July 1.

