#### 9.4.9.2 Missing AE Dates

If the start date or time of an AE is partially or completely missing and the end (stop) date or time of the AE does not indicate that it occurred prior to the first dose or the end date or time does not indicate that it occurred prior to the first dose, then treatment-emergence will be determined as follows:

- If the start year is after the year of the first study drug dose, then the AE is treatment-emergent; else,
- If the start year is the same as the year of the first study drug dose and
  - the start month is missing, then the AE is treatment emergent; else if
  - the start month is present and is the same or after the month of the first study drug dose, then the AE is treatment-emergent; else.
- If the start date is completely missing, then the AE is treatment-emergent.
- If the start date is the same as the date of the first study drug dose and start time is missing, then the AE is treatment-emergent.

To be able to calculate time from first dose to AE, the following are rules to input AE start dates:

Imputation Rules for Partial Dates (D = day, M = month, Y = year)			
Parameter	Missing	Additional Conditions	Imputation
Start date for AEs	D	M and Y same as M and Y of first dose of study drug	Date of first dose of study drug
		M and/or Y not same as date of first dose of study drug	First day of month
	D and M	Y same as Y of first dose of study drug	Date of first dose of study drug
		Y is after Y of first dose	Set to Jan 1st
	D, M, Y	None - date is completely missing	Date of first dose of study drug

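### By-visit growth summaries labelled FAS cover only children alive and assessed, so they can drift upward as poorly growing children die

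*SAP*

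**What the plan says.** SAP 7.3 places efficacy on the FAS, which SAP 6.1 defines as every child who received any study drug. For continuous endpoints it says that "the observed values, change from baseline and percent change from baseline at each time of assessment will be summarized". SAP 7 sets the convention for those summaries: "Continuous numeric endpoints will be summarized by providing the number of subjects with non-missing data", followed by the mean, SD and quantiles. SAP 7.3.1.4 applies this to growth, with observed z-scores and percentiles at each visit and their change from baseline.

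On missing values, SAP 7.3.1 states "All data will be analyzed as they were collected in the database. Missing data in general will not be imputed", and refers any exceptions to Section 9. Section 9 contains two imputation rules, and both concern dates. One is for partial dates under the age table ("In cases where only the month and year are provided for a date, the day for the date will be imputed as 15"). The other is for adverse events ("To be able to calculate time from first dose to AE, the following are rules to input AE start dates"). Protocol 8.13 says only "All data will be analyzed as they were collected in the database". Neither document says how a death enters a growth summary.

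For percentages, SAP 7 keeps children with missing data in the denominator, and Protocol 8.1 likewise uses the number treated. SAP 7.3.1.4 gives no exception for the underweight, stunting and wasting tables.

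Protocol 3.2.2.2 names growth failure among the main contributors to mortality and adds: "Improvement in growth is anticipated to be a prerequisite for any beneficial effects of sebelipase alfa on survival".

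**The concern.** The title population and the actual population of the growth tables differ. A table headed FAS contains, at each visit, only the children with a value at that visit. By the protocol's own reasoning, children who die are more likely to be those who were growing poorly. As they leave, the mean of the remaining children can rise although nobody has grown better. A reader comparing Week 48 with Week 12 could take the rise for treatment response, and the trial has no control arm against which to judge it.

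The growth-status percentages have a related gap. A dead child still counts in the denominator but can no longer be classified as underweight, stunted or wasted. Deaths of affected children therefore lower the percentage and look like improvement.

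**Working it through.** The plan states no figure to reproduce: enrolment of up to 10 is by feasibility (Protocol 8.2, SAP 9.3), and no on-treatment death rate is given. Mortality, the growth-survival correlation, the SD and the example z-scores below are assumptions.

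**1. Mean change across visits, nobody improving.** Take 10 children, 7 with change 0 and 3 with change -1.5 z.
- Before any death: (7 × 0 + 3 × (-1.5)) / 10 = -0.45 z.
- After those 3 die: (7 × 0) / 7 = 0.00 z.

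The table moves up by 0.45 z, but only as far as zero.

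**2. Observed z-scores, nobody changing.** Let weight-for-age z be evenly spaced from -4.5 to 0 in steps of 0.5, and let the lowest die first. The mean is -2.25 with no deaths, -1.75 after 2 and -1.25 after 4. The mean change from baseline among those left is 0 throughout.

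**3. Percent underweight in the same example** (z below -2; five children at the start).

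| Deaths | Planned rule | Among alive | Underweight or died, over FAS |
|---|---|---|---|
| 0 | 5/10 = 50% | 5/10 = 50% | 5/10 = 50% |
| 2 | 3/10 = 30% | 3/8 = 37.5% | (3 + 2)/10 = 50% |
| 4 | 1/10 = 10% | 1/6 = 16.7% | (1 + 4)/10 = 50% |

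With 10 children, each death of an underweight child takes 10 percentage points off the planned figure.

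**4. Expected shift in mean change.** Let change be normal with mean 0 and SD σ, correlated ρ with a latent survival score, and let the lowest fraction p of that score die. The expected mean change among survivors is

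shift = ρ × σ × φ(z_p) / (1 - p), where z_p is the p-quantile of the standard normal and φ its density.

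For σ = 1 the factor φ(z_p)/(1 - p) is 0.195, 0.350, 0.497 and 0.644 at p = 10%, 20%, 30% and 40%. The standard errors are averages over simulated cohorts of 10.

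| ρ | Deaths | Shift (z) | SE | Shift / SE |
|---|---|---|---|---|
| 0.5 | 10% | 0.10 | 0.31 | 0.3 |
| 0.5 | 20% | 0.18 | 0.32 | 0.55 |
| 0.5 | 30% | 0.25 | 0.34 | 0.7 |
| 0.5 | 40% | 0.32 | 0.37 | 0.9 |
| 0.7 | 30% | 0.35 | 0.32 | 1.1 |

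The shift scales with the SD. With σ = 1.5, ρ = 0.5 and exactly 1, 2, 3 or 4 deaths among 10, simulation gives +0.13, +0.24, +0.34 and +0.45 z.

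**The case against.** The strongest reply is that change from baseline is computed within each child (SAP 9.4.8.2). A reader might infer that deaths alone can produce a mean gain. They cannot: deaths of decliners lift a negative mean towards zero, and a positive mean requires that assessed children really gained. Calling the planned mean biased also needs a z-score for a dead child, which the simulation supplies by assumption. Read as a mean over children alive and assessed, the planned figure is correct. All of this stands.

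A reader might also take it as fact that the children who die are those who grew worst. The protocol calls growth failure one of several main contributors, and the prerequisite is only anticipated. Protocol 1.1.2 names severe hepatic disease as well, and Protocol 3.2.2.1 says growth failure need not be confirmed for entry. The direction is therefore expected, not established.

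Extending the argument to AST, ALT and ferritin is tempting, since their tables also use non-missing values. But the protocol text cited links growth to death, not changes in these analytes, and for transaminases the favourable direction is downward.

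Attrition is also partly visible: non-missing n, subject listings, disposition with reasons, a deaths listing, growth plotted on standard curves, and a separate survival analysis. With about 10 children, a careful reader can trace who died. This limits the harm. It does not correct the tabulated means or percentages, and n alone does not separate death from withdrawal or a missed measurement.

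Finally, a summary ranking death worst combines growth with survival, which Protocol 2.2 lists as separate objectives. That is why it should supplement the planned means and not replace them.

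**Conclusion.** The point holds for the growth endpoints. The by-visit z-score tables carry the FAS label but describe children alive and assessed. Their observed means, and mean changes compared across visits, can drift upward through deaths alone.

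The effect on mean change is modest under the assumed inputs: about 0.1 to 0.2 z at 10% to 20% deaths with correlation 0.5. It approaches one standard error only at 40% deaths, or at 30% with correlation 0.7. One death among 10 matters little; three or more can matter. These sizes rest on assumed mortality, correlation and SD.

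The growth-status percentages need no correlation assumption: under the stated denominator rule, every death of an affected child lowers the figure.

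All analyses are descriptive and safety is the primary objective, so this is not a matter of type I error or of the primary result. It concerns what the growth tables can be taken to show, and it is cheap to put right.

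**What to change.** In SAP 7.3.1.4:

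- Keep the planned means and label them 'among children alive and assessed'.
- Under each by-visit growth table, show the numbers alive and assessed, alive and not assessed, died, and off study.
- Add a supplementary summary for weight-for-age, weight-for-length/height and length/height-for-age z-scores at Week 48, and at Week 96 where data permit: the median change over the FAS with deaths ranked worst. State how children alive but unassessed are handled, for example excluded with the count shown, plus a worst-case and best-case range. The median is estimable while fewer than half of the children ranked have died. Week 96 needs the caveat because treatment is expected to last at least 18 months, about 78 weeks (1.5 × 52), so a living child may have no Week 96 value.
- Report underweight, stunting and wasting both among children alive and assessed and as 'affected or died' over the FAS.
- Leave AST, ALT and ferritin out of the death-ranked summary.

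The cost is SAP wording and a few table rows. No new data are needed, since Protocol 4.6.2 already collects the survival status of discontinued children until the study ends. The downside is a less favourable growth summary beside the planned one.
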